2.3 Benefit/Risk Assessment

TER-101 was safe and well tolerated when administered as a topical ointment (1.0% w/w) twice daily for up to 2 weeks to healthy volunteer subjects (n=8) and patients (n=28) with moderate to severe AD. The most common treatment emergent adverse events (TEAEs) in TER-101 treated subjects were local application site events including pruritus, dry skin, and dermatitis. The majority of reported TEAEs in healthy volunteers or subjects with AD were mild to moderate in

severity. Three of 10 subjects with moderate to severe AD randomized to the vehicle arm withdrew due to TEAEs related to lack of efficacy. No healthy volunteers or subjects with AD treated with TER-101 withdrew from the study. There were no clinically significant safety concerns identified in vital signs, physical examinations, electrocardiograms (ECGs), or clinical laboratory assessments.

In this small study, there was no statistically significant difference in the primary efficacy analysis (percentage change from baseline in Eczema Area and Severity Index [EASI] score at Week 2) or in a sensitivity analysis using multiple imputation, between the TER-101 and placebo groups. In the sensitivity analysis using last observation carried forward, there was evidence of a trend towards a larger decrease in EASI scores and other efficacy assessments in the TER-101 compared with the placebo group. This result was also supported by the worst-case imputation sensitivity analysis. Three patients in the TER-101 group were assessed as EASI-75 (75% reduction in EASI score from baseline) responders. No patients in the placebo group met this definition. A trend towards greater improvement in the TER-101 group was also evident in the Patient Global Impression of Change assessment.

Teres Bio anticipates the most likely TEAE in the Phase 2 upcoming study will be local application site TEAEs including pruritus, dry skin, stinging/burning, pain, or dermatitis including atopic dermatitis. The protocol includes rules for treatment cessation in the event that subjects develop severe local TEAEs or high scores on the tolerability assessments. Once local AEs have abated, treatment may be re-initiated once daily. Teres Bio believes that the accrued clinical safety and preliminary efficacy data support a favorable benefit-risk profile for the proposed protocol and that appropriate monitoring and stopping rules have been included in the planned study design.

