6.6.1 Rescue Medication

Use of rescue medication is not permitted in this study. Any subject requiring rescue therapy per investigator opinion should undergo the early termination visit consisting of the Day 29 assessments and be withdrawn from the study prior to receiving rescue therapy.

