9.4.1 General Considerations

Disposition, analysis populations, demography, baseline characteristics, medical history, and concomitant medication data will be summarized overall and by treatment, where applicable.

Efficacy endpoints will be summarized by treatment and visit. For the efficacy endpoints that are collected longitudinally, a last observation analysis will be performed by carrying forward the last post-baseline assessment. These last observation carried forward (LOCF) analyses guarantee the maximum number of randomized patients who were assessed post-baseline will be included in the analyses. In addition, for continuous efficacy endpoints, mixed effect model repeated measures (MMRM) analyses will be performed to mitigate the impact of missing data, which will be assumed to be missing at random during the study. Continuous and score data will be summarized using descriptive statistics (eg, mean and standard deviation or standard error). Categorical and dichotomous data will be summarized using frequency tables (counts and percentages).

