9.7 Handling of Missing Data

All possible efforts will be made to ensure that subjects complete study treatments and all the required assessments. However, in the rare case of subjects discontinuing from study treatment or discontinuing from the study, all attempts will be made to perform all efficacy and safety assessments at the time of discontinuing study treatment or study in order to minimize missing data.

The number of subjects with missing efficacy data at Day 15 and Day 29 visits will be presented as missing for TER-101 or vehicle, together with a summary of the reasons for the missing data. Missing efficacy data will be classified as missing at random (not informative) or missing not at random (informative eg, due to treatment-related discontinuation such as lack of efficacy or an AE), and documented prior to database lock and unblinding.

As missing efficacy data may potentially bias the outcome of the statistical analyses and the subsequent estimation of the magnitude of the treatment effect, different strategies will be applied to provide a balanced assessment of treatment efficacy. The handling of missing data, including consideration of imputing values for missing data, for each efficacy endpoint and sensitivity analyses will be detailed in the SAP prior to the study database lock and unblinding.

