1.2 SAMPLE SIZE

The sample size is based on a clinical rather than statistical rationale. Approximately 60 subjects are planned to be enrolled and randomized, considering a potential 15% drop-out rate, to yield approximately 50 subjects completing the study.

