3.1 GENERAL STATISTICAL CONSIDERATIONS

Descriptive statistics (mean, standard deviation [Std Dev], median, minimum, and maximum) will be used for continuous variables; number and percentage of subjects will be used for discrete variables. In general, the last measurement prior to the first dose of study treatment will be used as the baseline value with exception of WI-NRS, where the score recorded on Day 1 describing the worst itch score 24 hours prior will be used as the baseline. Nominal visits will be used for by-visit summaries and analyses for safety evaluations (i.e., laboratory sampling, physical examinations, vital signs, and electrocardiogram). For efficacy evaluations of EASI, IGA, and TBSA, analysis visits will be used for by-visit summaries. Analysis visits are defined as below:

Analysis Visit*	Target Day	Range
Day 8	Day 8	Day 2 – Day 11
Day 15	Day 15	Day 12 – Day 21
Day 29	Day 29	≥Day 22

* If there are multiple observations in the range, then the record collected closest to the target day will be selected; if there are multiple observations that have equal distance from the target day, the latter one will be used.

All treatment group comparisons will be made at the 0.05 level using a two-sided hypothesis test, unless otherwise specified. Given the exploratory nature of this study, p-values from all significance tests will be reported without adjustment for multiplicity.

Summaries will be presented by each treatment group, ie, TER-101 2.75% ointment, Vehicle ointment.

All tabulations of summary statistics, graphical presentations, and statistical analyses will be performed using SAS[®] Version 9.4 or higher.

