- Last value carried forward (LOCF): for timepoint Day 29, if missing, the last available post baseline EASI total score will be carried forward to the timepoint. After this imputation, an analysis of covariance (ANCOVA) will be used for analyzing the treatment effect at Day 29. The treatment group will be the fixed effect and baseline score will be the covariate. The treatment difference, 95% confidence limits, and p-value will be presented.
- Return to baseline: missing Day 29 value will be imputed based on the baseline value for the patient, with variance adjustment of the Day 29 EASI total score. That is, the missing data will be imputed with values from Normal distribution $N(\text{baseline}_i, \sigma_k^2)$; i = i th subject, where σ_k^2 is the variance estimate of treatment k at Day 29. Five hundred (500) imputation will be implemented. ANCOVA model will be used for each imputation. The results from all imputed datasets will be combined using Rubin's combination rule (PROC MIANALYZE).

In addition, the percent change from baseline in EASI scores and the absolute change from baseline in EASI total score by each region will be analyzed using the MMRM model, as described above. In each case, the treatment p-value (TER-101 2.75% vs. vehicle), treatment difference, and 95% confidence limits from the model, will be presented.

The effect of treatment on response rates (EASI-75, EASI-50) at each visit will be evaluated using a logistic generalized linear mixed model (GLMM) for binary data. The model will include fixed effect for treatment, visit and treatment-by-visit interaction, with subject nested within the investigational site as a random effect. The treatment p-value (TER-101 2.75% vs. vehicle), treatment odds ratio, and 95% confidence limits from the model, will be presented. [Note: In the event of model non-convergence, the response proportions will be analyzed using the Cochran-Mantel-Haenszel test, stratified by baseline IGA.] Bar charts of the response rates at Day 15 and Day 29 will be presented by treatment groups for each response rate (EASI-75, EASI-50).

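### The SAP gives withdrawn subjects no response status in the EASI-50/75 and itch-responder analyses, so a treatment failure before Day 22 has no Day 29 EASI response

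*SAP*

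**What the plan says.** - **EASI-50/75.** SAP 3.6.1: "The effect of treatment on response rates (EASI-75, EASI-50) at each visit will be evaluated using a logistic generalized linear mixed model (GLMM". The model uses Day 15 and Day 29, with subject within site as a random effect. If it fails to converge, a Cochran-Mantel-Haenszel (CMH) test replaces it. Bar charts show the rates at both visits. No rule covers a missing response.
- **Itch responder.** SAP 3.6.3 uses logistic regression and a chi-square test in subjects with baseline WI-NRS of at least 4. It names no time point for that comparison and no handling of missing scores.
- **Sensitivity analyses.** The two in SAP 3.6.1 (LOCF and return to baseline) apply only to percent change in EASI at Day 29.
- **Withdrawal.** Under Protocol 6.6.1 a subject needing rescue has the Day 29 assessments at an early termination visit and must then "be withdrawn from the study prior to receiving rescue therapy". Protocol 7.2 ends treatment and study participation together, so no later visits follow.
- **Windows.** SAP 3.1 assigns EASI by study day: Days 2–11 to Day 8, Days 12–21 to Day 15, Day 22 onward to Day 29. Within a window the record nearest the target day is kept.
- **Missing data in the protocol.** Section 9.7 recognises a class of data "missing not at random (informative eg, due to treatment-related discontinuation such as lack of efficacy or an AE" and leaves the handling for each efficacy endpoint to the SAP. Section 9.4.1 says that for longitudinally collected efficacy endpoints "a last observation analysis will be performed by carrying forward the last post-baseline assessment". SAP section 4 lists three changes; dropping LOCF for the responder endpoints is not among them.

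**The concern.** A subject who leaves because of a flare, need for rescue or intolerance has failed treatment in any ordinary reading of a response rate. Under the SAP, whether that failure is seen at Day 29 depends on the calendar day of withdrawal, and for most days it is not seen. A likelihood-based mixed model with no further rule is valid only if the missing responses are missing at random, which is not how the protocol classifies missingness due to treatment-related discontinuation. The bar charts, the CMH fallback and the itch regression lack even the partial protection of a repeated-measures model.

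If failures are mainly on vehicle, leaving them out understates the drug's effect. If they are mainly intolerance on TER-101, it overstates the effect. There is precedent for imbalance. In the earlier 1% study, "Three of 10 subjects with moderate to severe AD randomized to the vehicle arm withdrew due to TEAEs related to lack of efficacy", while no TER-101 subject withdrew (Protocol 2.3). In that study the reading also shifted with the missing-data method: the primary and multiple-imputation analyses showed no significant difference, whereas LOCF and worst-case imputation pointed to a trend.

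**Working it through.** **1. The plan's own figure.** SAP 1.2 plans about 60 subjects, "considering a potential 15% drop-out rate, to yield approximately 50 subjects completing the study". 60 × (1 − 0.15) = 51, and 50 / 0.85 = 58.8, so 59. The figures agree. No response rate or power is given ("The sample size is based on a clinical rather than statistical rationale"), so the response rates below are assumptions.

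**2. Where an early termination visit lands (EASI).** Withdrawal can fall on Days 2–28, which is 27 days.
- Days 2–11 (10 days): Day 8 window, which is not in the model.
- Days 12–21 (10 days): Day 15 window, where the visit can lose to one closer to Day 15. Day 29 stays empty.
- Days 22–28 (7 days): Day 29 window, scored as observed.

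If withdrawals are spread evenly (assumption), 7/27 = 26% are scored at Day 29 and 20/27 = 74% are not.

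**3. Formulas.** Let p be the response rate among completers and d the proportion withdrawn for failure. Every withdrawn subject is assumed to be a non-responder and to attend an early termination visit.
- No withdrawn subject scored: p
- SAP windows: p(1 − d) / [(1 − d) + (7/27)d]
- Failures counted: p(1 − d)

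Example, vehicle, p = 30%, d = 30%: SAP windows 0.21 / (0.70 + 0.078) = 27.0%; failures counted 0.30 × 0.70 = 21.0%.

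**4. Results**, p = 50% on TER-101 and 30% on vehicle (differences in percentage points):

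| Withdrawn, TER-101 / vehicle | None scored | SAP windows | Failures counted | SAP windows minus failures counted |
|---|---|---|---|---|
| 15% / 15% | 20.0 | 47.8 − 28.7 = 19.1 | 42.5 − 25.5 = 17.0 | +2.1 |
| 0% / 30% | 20.0 | 50.0 − 27.0 = 23.0 | 50.0 − 21.0 = 29.0 | −6.0 |
| 30% / 0% | 20.0 | 45.0 − 30.0 = 15.0 | 35.0 − 30.0 = 5.0 | +10.0 |
| 10% / 20% | 20.0 | 48.6 − 28.2 = 20.4 | 45.0 − 24.0 = 21.0 | −0.6 |
| 20% / 10% | 20.0 | 47.0 − 29.2 = 17.8 | 40.0 − 27.0 = 13.0 | +4.8 |

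The second row is the earlier study's pattern; at 30 per arm it is 9/60 = 15% overall, the planned dropout. Odds ratios (SAP windows, then failures counted) in the first three rows are 2.28 and 2.16, 2.70 and 3.76, 1.91 and 1.26.

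**5. Itch.** The SAP 3.1 windows do not cover WI-NRS. If response is read on a fixed day, a subject withdrawn earlier has no score, so the column with none scored applies. It differs from failures counted by 20.0 − 17.0 = 3.0, 20.0 − 29.0 = −9.0 and 20.0 − 5.0 = 15.0 points in the first three rows.

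**6. Equal completer rates (30% in each arm).** At 0% / 30% the SAP windows give +3.0 points and counting failures gives +9.0; at 30% / 0% the signs reverse.

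**The case against.** - **A reader might infer that the plan never counts a withdrawn subject as a non-responder.** The documents do not support that. An early termination visit from Day 22 on that misses the threshold is an observed non-response at Day 29. An earlier leaver's Day 15 response also stays in the GLMM.
- **Observed-case handling is not written down.** The counts in SAP 3.6.1 and the itch analysis are both on the efficacy set (ES) and could be read with the full set as denominator. That is fair for the descriptive rates, but it means the denominator is undefined. It does not help the GLMM, which cannot use an absent response.
- **LOCF would not solve the problem.** Protocol 9.4.6 ties LOCF and multiple imputation to the primary endpoint and itself specifies the GLMM for EASI-50/75. LOCF would also carry a Day 15 responder forward as a responder after withdrawal. Both points stand. The lost LOCF is an unlisted departure from Protocol 9.4.1, not an argument for the remedy.
- **Counting every AE withdrawal as failure is a choice of estimand.** Protocol 9.7 speaks of treatment-related discontinuation, and an unrelated AE can remove a true responder. This stands, and is a reason to keep the planned model alongside.
- **Importance.** The endpoints are secondary, the study is exploratory with unadjusted p-values, Protocol 7.2 expects withdrawal to be uncommon, and the primary endpoint has its own sensitivity analyses. All true; this limits the weight of the point without removing it.

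**Conclusion.** The gap is real. The SAP leaves response after withdrawal undefined for EASI-50/75 and itch, although Protocol 9.7 deferred exactly this to it, and a withdrawal before Day 22 leaves the Day 29 EASI response empty.

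A reader might infer that the response comparison is biased, or that the drug's effect will be understated. Neither is shown. Bias is a risk whose direction depends on which arm loses more subjects to failure. After crediting visits from Day 22, the difference is off by about 2 points at equal 15% dropout, 0.6 to 4.8 points under the 10%/20% patterns, and 6 to 10 points under the 0%/30% patterns.

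These figures are arithmetic on proportions, not a GLMM fit. They assume 50% against 30% completer response, even timing of withdrawal, and non-response in everyone withdrawn. The 0%/30% pattern rests on 3 of 10 vehicle subjects with moderate to severe disease, more severe than the population here. The change is worth making but does not touch the primary analysis.

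**What to change.** Before unblinding, amend the SAP as follows.

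1. In 3.6.1 and 3.6.3, add a responder analysis in which subjects withdrawn for rescue need, lack of efficacy or an AE are non-responders at all visits after withdrawal. The denominator is all ES subjects in the arm (for WI-NRS, those with baseline of at least 4).
2. Use this definition for the bar charts and for the CMH and logistic comparisons. Keep the observed-case GLMM alongside it.
3. State that responses missing for other reasons, such as loss to follow-up, are treated as missing at random, with a sensitivity analysis counting them as non-responses.
4. Name the WI-NRS responder time points: Day 15 and Day 28, as in the SAP's own WI-NRS MMRM.
5. List in section 4 that the LOCF of Protocol 9.4.1 is not carried over to the responder endpoints.

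The cost is SAP wording and a little programming. Reasons for discontinuation are already collected and summarised (Protocol 7.1, SAP 3.2.3), and nothing in the conduct of the trial changes. Reported response rates become somewhat lower; at 15% withdrawn in both arms, the assumed 50% and 30% become 42.5% and 25.5%.

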9.4.6 Efficacy Analyses

The primary endpoint (percent change from baseline in EASI total score) will be analyzed using a mixed model for repeated measures (MMRM). The model will include fixed effect for study treatment (TER-101 2.75%, vehicle), visit day (Day 15, Day 29), and treatment-by-visit interaction, with visit as the repeating factor, subject as a random effect, and baseline score as a covariate. The treatment p-value (TER-101 2.75% vs. vehicle), treatment difference, and 95% confidence limits from the model will be presented for the percent change from baseline in EASI at Day 29. Sensitivity analyses will include analysis of covariance (ANCOVA) at each timepoint. The impact of dropouts and missing data on results for the primary endpoint will be explored using the last value carried forward (LOCF) and multiple imputation methods, as appropriate.

Secondary efficacy endpoints that are continuous variables (percent change from baseline in EASI component scores, absolute change from baseline in EASI, IGA, TBSA, and WI-NRS) will also be analyzed using the MMRM model, as described above. In each case, the treatment p-value (TER-101 2.75% vs. vehicle), treatment difference, and 95% confidence limits from the model, will be presented.

The effect of treatment on response rates (75% reduction in EAI Score [EASI-75], 50% reduction in EASI scores [EASI-50]) at each visit will be evaluated using a logistic generalized linear mixed model (GLMM) for binary data, with fixed effect for treatment, visit and treatment-by-visit interaction. The treatment p-value (TER-101 2.75% vs. vehicle), treatment odds ratio, and 95% confidence limits from the model, will be presented. [Note: In the event of model non-convergence, the response proportions will be analyzed using the Cochran-Mantel-Haenszel test, stratified by baseline IGA.] The proportion of WI-NRS responders (defined by a reduction of ≥ 3 in subjects with baseline WI-NRS ≥ 4) will be analyzed using a chi-square test.

Time to onset of response (EASI 75, EASI-50) will be estimated using the Kaplan-Meier method, with treatment comparisons based on the logrank test. Subjects who do not achieve response criteria will be censored on the day of last assessment.

Given the exploratory nature of this study, p-values from all significance tests will be reported without adjustment for multiplicity.

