3.6.1 EASI Analyses

For each visit (baseline, Day 15, Day 29), the following analyses will be performed. All analyses will be based on the ES.

- Descriptive statistics (n, mean, Std Dev, median, minimum, and maximum) will be provided for the per-subject EASI total score (continuous), change from baseline, and percent change from baseline in EASI total score.
- Descriptive statistics (n, %) will be provided for the number and percentage of subjects who achieve EASI-50 (i.e., ≥50% reduction from baseline) and EAST-75 (i.e., ≥75%).

Descriptive statistics (n, mean, Std Dev, median, minimum, and maximum) will be provided for the per-subject EASI by region (head, trunk, upper extremity [UE], lower extremity [LE]), change from baseline, and percent change from baseline values. Treatment group comparisons

in percent change from baseline in EASI total score will be analyzed using a mixed model for repeated measures (MMRM). The model will include fixed effect for study treatment (TER-101 2.75%, vehicle), visit day (Day 15, Day 29), and treatment-by-visit interaction, with visit as the repeating factor, subject nested within the investigational site as a random effect, and baseline score as a covariate. The variance-covariance matrix will be assumed to be unstructured. If the procedure does not converge then the replacement of variance-covariance matrix will be explored in the order of Toeplitz, first-order autoregressive, compound symmetric. The treatment p-value (TER-101 2.75% vs. vehicle), treatment difference, and 95% confidence limits from the model will be presented for the percent change from baseline in EASI at Day 29. Similarly, the treatment difference (TER-101 2.75% vs. vehicle) and 95% confidence limits will be presented for Day 15 as well. Line graphs of least squares mean in percent change from baseline of EASI scores will be presented for Day 15 and Day 29. These treatment group comparisons will be repeated for the PPES.

The following sensitivity analyses will be conducted for the percent change from baseline in EASI total score at Day 29 to explore the impact of dropouts and missing data at Day 29.

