3.6.3 WI-NRS Analyses

Descriptive statistics (n, mean, Std Dev, median, minimum, and maximum) will be provided for the 11-point WI-NRS scale at baseline, Day 15 and Day 28 visits, and its change from baseline at Day 15 and Day 28. A line plot over time of the change from baseline (daily, and weekly average [see intervals specified below]) will be generated. Mean (\pm Std Dev) will be displayed at each time point. Change from baseline WI-NRS scale will also be analyzed using the MMRM model for Day 15 and Day 28 assessments. The model will include fixed effect for study treatment (TER-101 2.75%, vehicle), visit day (Day 15, Day 28), and treatment-by-visit interaction, with visit as the repeating factor, subject within the investigational site as a random effect, and baseline WI-NRS scale as a covariate. The treatment p-value (TER-101 2.75% vs. vehicle), treatment difference, and 95% confidence limits from the model, will be presented.

The proportion of WI-NRS responders (defined by a reduction of ≥ 3 in subjects with baseline WI-NRS ≥ 4) will be analyzed using a logistic regression. The odds ratio, and 95% confidence limits from the model, will be presented. The chi-square test p-value will also be provided. In addition, the number and percentage of subjects who respond during each weekly interval (defined by the maximum reduction between Day 2-Day 8, Day 9-Day 15, Day 16-Day 22, Day 23-Day 28) will be summarized and presented in a bar chart.

All analyses will be based on ES.

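### The EASI-50/75 and WI-NRS responder models list no baseline term, unlike the SAP's other efficacy models and the EASI model's own fallback

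*SAP*

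**What the plan says.** **EASI-50/75.** SAP 3.6.1: "The model will include fixed effect for treatment, visit and treatment-by-visit interaction", plus a random effect for subject within site. Protocol 9.4.6 lists the same terms: "with fixed effect for treatment, visit and treatment-by-visit interaction". Neither includes baseline EASI or IGA. If the model does not converge, "the response proportions will be analyzed using the Cochran-Mantel-Haenszel test, stratified by baseline IGA".

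**WI-NRS responders.** SAP 3.6.3 says that the proportion with a fall of at least 3, among subjects starting at 4 or more, "will be analyzed using a logistic regression", and lists no model terms. It adds: "The chi-square test p-value will also be provided". Protocol 9.4.6 planned only the chi-square test.

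**The other efficacy models.**
- EASI percent change (MMRM, SAP 3.6.1): "subject nested within the investigational site as a random effect, and baseline score as a covariate". The regional EASI analyses reuse this model.
- LOCF ANCOVA (SAP 3.6.1): "The treatment group will be the fixed effect and baseline score will be the covariate".
- WI-NRS change (3.6.3) and TBSA change (3.6.4): each MMRM includes its own baseline value.
- IGA change (3.6.2): the cumulative-logit model includes baseline IGA.

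SAP section 4, on changes to planned analyses, gives no reason for treating the responder models differently.

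**The concern.** There are two separate issues.

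**Internal consistency.** The fallback shows that the plan regards baseline severity as worth adjusting for. As written, though, an EASI-50 or EASI-75 comparison is adjusted only if the mixed model fails, so a numerical property of the data decides which kind of result is reported. Avoiding covariates in logit models cannot be the explanation, because the IGA model is of that type and has one.

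**Prognostic information left unused.** The WI-NRS response is an absolute fall, so the same 3 points is a different demand at different starting scores. About 60 subjects are randomized, and neither Protocol 6.4.1 nor SAP 2.3.2 describes a stratification factor. A chance difference between arms in starting score can therefore affect the observed comparison. At stake are some power and the ease of interpreting secondary endpoints in an exploratory trial.

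**Working it through.** **Step 1. The plan's own figure.** The only sizing figure is about 60 randomized, 15% dropout and about 50 completers (SAP 1.2). 60 x (1 - 0.15) = 51, which agrees. With 1:1 allocation that is about 25 completers per arm. No power, responder rate or baseline-response association is given.

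**Step 2. WI-NRS arithmetic.** A subject starting at 4 must reach 4 - 3 = 1 or less, a 75% fall. A subject starting at 10 need only reach 10 - 3 = 7, a 30% fall. The definition makes dependence on the starting score possible; the documents do not show how strong it is.

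**Step 3. Size of chance imbalance.** With n per arm, the standard error of the between-arm difference in mean baseline is sqrt(2/n) in SD units. For n = 25 it is sqrt(2/25) = 0.28. For n = 22 (an assumed number per arm with baseline WI-NRS of at least 4) it is sqrt(2/22) = 0.30.

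**Step 4. Simulated effect of adding baseline.** Single-visit logistic regression was run with and without a baseline covariate: two-sided 0.05 likelihood-ratio test, 4,000 trials per scenario, Monte Carlo error about 0.8 points. All response rates and associations are assumptions. EASI rows use 25 per arm and a continuous covariate; WI-NRS rows use 22 per arm.

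| Scenario (assumed rates) | Baseline association | Power without, with | Change (points) | SE of log OR without, with |
|---|---|---|---|---|
| EASI-50-like, 30% vs 60% | 0 | 62.7%, 60.3% | -2.4 | 0.617, 0.635 |
| | 0.2 | 63.8%, 62.0% | -1.8 | 0.620, 0.650 |
| | 0.3 | 61.6%, 62.1% | +0.5 | 0.618, 0.664 |
| | 0.5 | 62.0%, 66.5% | +4.5 | 0.619, 0.731 |
| EASI-75-like, 10% vs 30% | 0 | 40.1%, 40.5% | +0.4 | 0.853, 0.874 |
| | 0.3 | 41.8%, 44.3% | +2.5 | 0.856, 0.908 |
| | 0.5 | 40.0%, 46.2% | +6.2 | 0.851, 0.971 |
| WI-NRS-like, about 31% vs 57% | about 0 | 41.4%, 42.6% | +1.2 | 0.654, 0.675 |
| | about 0.23 | 38.6%, 41.6% | +3.0 | 0.652, 0.702 |
| | about 0.33 | 37.2%, 42.7% | +5.5 | 0.648, 0.734 |

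The association is a latent correlation for the EASI rows and the baseline-response correlation in the vehicle arm for WI-NRS. Further WI-NRS runs at 22 per arm, with other assumed baseline effects, reached a gain of about 7 points. About 7% of EASI-75-like trials gave no finite estimate.

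**Step 5. Why power can rise while the SE also rises.** Adjustment moves the conditional log odds ratio away from zero as well as widening its SE. WI-NRS at about 0.33: 1.042/0.648 = 1.61 without baseline, 1.243/0.734 = 1.69 with it. EASI-50-like at 0: 1.311/0.617 = 2.12 without, 1.344/0.635 = 2.12 with, so nothing is gained.

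**Step 6. Type I error.** With equal response rates, EASI-like rejection was 4.8-5.6% without baseline and 5.4-5.9% with it. For WI-NRS it was 5.0-5.7% and 5.2-5.9%.

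**The case against.** The strongest reply is that the EASI specification is a defensible choice. Its fixed effects match the protocol. The endpoint is already a percentage reduction from baseline, and entry is limited to IGA 2-3, EASI of at least 5 and TBSA 2-30%, so baseline may carry little further information. With about 25 completers per arm and possibly few EASI-75 responders, a leaner model is reasonable. These are exploratory secondary endpoints. Crude EASI-50/75 rates by visit and weekly WI-NRS responder rates are already planned. All of this stands, and it limits the point to a minor one. It does not explain why the fallback adjusts and the main model does not.

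Three stronger readings are tempting, and the documents do not support them.
- *The responder models give up precision at no saving.* The plan reports odds ratios. Adding baseline widened the SE of the log odds ratio in every scenario, and it carries some sparse-data cost.
- *The unadjusted comparison is invalid.* Chance imbalance is already allowed for by the test, and type I error was near 5% without adjustment.
- *The SAP specifies an unadjusted WI-NRS model while every continuous model is adjusted.* For WI-NRS the SAP is silent on model terms, and the return-to-baseline ANCOVA does not restate its covariates either.

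**Conclusion.** The point holds as a minor one. The inconsistency between the EASI responder model and its fallback is plain from the text and needs no simulation. The WI-NRS model needs its covariates stated, and baseline WI-NRS is the natural one.

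The expected benefit is modest: about +1 to +7 power points for WI-NRS and about -2 to +6 for EASI-50/75, with type I error near 5-6%. These figures rest on assumed response rates, assumed numbers per arm and an assumed baseline effect, none of which the documents give. The two-visit mixed model was not simulated. The EASI runs used a continuous covariate; eligibility leaves baseline IGA with only two levels, so an IGA term would probably capture less. For EASI the main reason to change is therefore consistency rather than power.

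**What to change.** Before unblinding, amend the SAP as follows.

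1. **WI-NRS responders (3.6.3):** add baseline WI-NRS as a covariate in the logistic regression, take the main p-value from that model, and keep the chi-square test as supportive.
2. **EASI-50 and EASI-75 (3.6.1):** add baseline IGA to both mixed models so that they match the "Cochran-Mantel-Haenszel test, stratified by baseline IGA". Keep the existing non-convergence rule as the only trigger for the fallback; do not add a judgement about responder counts, which would make the choice depend on the data.
3. **Reporting:** show crude response rates and a risk difference beside each odds ratio, and label the odds ratio as conditional on baseline. The EASI crude rates are already planned, so the risk difference is the main addition.

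The cost is a few lines of SAP text and one term per model, with no new data. The odds ratio becomes conditional on baseline (the EASI mixed-model odds ratio is already conditional on the subject effect), its interval on the log scale widens, and the extra term slightly raises the sparse-data risk for EASI-75.
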